11.3.4 Secondary analyses

11.3.4.1 OS analyses

Table 11.3.4.1.1 OS (“All Randomized Patients” population)

	Arm A	Arm B	Parameter	p-value
N				
Events				
Censored				
Median OS			Log-Rank: HR (95% CI) :	LR: HR:
OS at 12 months			Diff:	
OS at 24 months			Diff:	

Kaplan-Meier plot will be also shown (Figure 11.3.4.1.1).

Table 11.3.4.1.2 OS stratified comparison (“All Randomized Patients” population)

	Arm A	Arm B
Stratum 1		
N		
Events		
Censored		
Median OS		
OS at 12 months		
OS at 24 months		
Stratum 2		
N		
Events		
....		
....		
Log-Rank* / p-value** / HR (95% CI) :		

(*)Stratified log-rank test statistic. (**) p-value from stratified log-rank test

Table 11.3.4.1.3 OS (“All Randomized Patients” population excluding crossover patients)

	Arm A	Arm B	Parameter	p-value
N				
Events				
Censored				
Median OS			Log-Rank: HR (95% CI) :	LR: HR:
OS at 12 months			Diff:	
OS at 24 months			Diff:	

Kaplan-Meier plot will be also shown (Figure 11.3.4.1.3).

Table 11.3.4.1.4 OS (“All Randomized Patients” population censoring crossover patients at cross-over date)

	Arm A	Arm B	Parameter	p-value
N				
Events				
Censored				
Median OS			Log-Rank: HR (95% CI) :	LR: HR:
OS at 12 months			Diff:	
OS at 24 months			Diff:	

Kaplan-Meier plot will be also shown (Figure 11.3.4.1.4).

Table 11.3.4.1.5 OS (“All Randomized Patients” population and IPCW method)

	Arm A	Arm B	Parameter	p-value
N				
Events				
Censored				
Median OS			Log-Rank: HR (95% CI) :	LR: HR:
OS at 12 months			Diff:	
OS at 24 months			Diff:	

Kaplan-Meier plot will be also shown (Figure 11.3.4.1.5).

Table 11.3.4.1.6 OS (“All Randomized Patients” population and RPSFT method)

	Arm A	Arm B	Parameter	p-value
N				
Events				
Censored				
Median OS			Log-Rank: HR (95% CI) :	LR: HR:
OS at 12 months			Diff:	
OS at 24 months			Diff:	

Kaplan-Meier plot will be also shown (Figure 11.3.4.1.6).

A forest plot (Figure 11.3.4.1.7) with the summary of hazard ratios for PFS and OS in the different analysis populations will be shown to check the consistency across the different measurements.

Table 11.3.4.1.8 OS – Reason of censoring (“All Randomized Patients” population)

Reason of censoring	Arm A		Arm B	
	N	%	N	%
Alive				
Lost to follow-up				
Withdrawal of consent				

Table 11.3.4.1.9 OS (Subpopulation without crossover or subsequent therapy)

	Arm A	Arm B	Parameter	p-value
N				
Events				
Censored				
Median OS			Log-Rank: HR (95% CI) :	LR: HR:
OS at 12 months			Diff:	
OS at 24 months			Diff:	

Kaplan-Meier plot will be also shown (Figure 11.3.4.1.9).

Table 11.3.4.1.10 OS (Subpopulation of patients with event in the primary analysis and without crossover or subsequent therapy)

	Arm A	Arm B	Parameter	p-value
N				
Events				
Censored				
Median OS			Log-Rank: HR (95% CI) :	LR: HR:
OS at 12 months			Diff:	
OS at 24 months			Diff:	

Kaplan-Meier plot will be also shown (Figure 11.3.4.1.10).

Table 11.3.4.1.11 OS (“All Randomized Patients” population and Two-stage method)

	Arm A	Arm B	Parameter	p-value
N				
Events				
Censored				
Median OS			Log-Rank: HR (95% CI) :	LR: HR:
OS at 12 months			Diff:	
OS at 24 months			Diff:	

Kaplan-Meier plot will be also shown (Figure 11.3.4.1.11).

A forest plot (Figure 11.3.4.1.12) with the summary of hazard ratios for OS in the different analysis populations will be shown to check the consistency across the different measurements.

Supportive analyses needed to adjust OS by crossover by the two-stage method

Table 11.3.4.1.13 Logistic regression (Crossover patients vs no crossover patients)

Analysis of Maximum Likelihood Estimates*								
Variable Label	Variable values	DF	Parameter Estimate	Standard Error	Chi-Square	Pr > ChiSq	Odds Ratio	95% Odds Ratio Confidence Limits

* Logistic regression

See list of covariates in section 6.2.3

Table 11.3.4.1.14 PFS (Crossover patients vs no crossover patients)

	Crossover	No crossover	Parameter	p-value
N				
Events				
Censored				
Median PFS			Log-Rank: HR (95% CI) :	LR: HR:

Kaplan-Meier plot will be also shown (Figure 11.3.4.1.14).

Table 11.3.4.1.15 Post progression survival (Weibull adjustment)

Analysis of Maximum Likelihood Parameter Estimates							
Parameter		DF	Estimate	Standard Error	95% Confidence Limits	Chi-Square	Pr > ChiSq
Intercept							
Treatment arm	-						
Treatment arm	Crossover						
Scale							
Weibull Shape							

11.3.4.2 Response rate by independent review committee

Table 11.3.4.2.1 Response rate by IMWG (Independent Review assessment and “All Randomized Patients” population)

Response	Arm A		Arm B	
	N	%	N	%
sCR				

CR				
VGPR				
PR				
MR				
SD				
PD				
Unknown*				

(*) Including NE and insufficient data available.

Table 11.3.4.2.2 Response rate estimates by IMWG (Independent Review assessment and “All Randomized Patients” population)

	Arm A			Arm B		
	Proportion	Lower 95% limit	Upper 95% limit	Proportion	Lower 95% limit	Upper 95% limit
Response rate						

Binomial exact estimator and 95% confidence interval

Table 11.3.4.2.3 Response rate comparison by IMWG (Independent Review assessment and “All Randomized Patients” population)

Response rate	Arm A		Arm B		Fisher exact test (p-value)
	N	%	N	%	
sCR+CR+VGPR+PR+MR					
SD+PD+UK*					

(*) Including NE and insufficient data available.

Table 11.3.4.2.4 Response rate by IMWG (Independent Review assessment and “All Evaluable Patients” population)

Response	Arm A		Arm B	
	N	%	N	%
sCR				
CR				
VGPR				
PR				
MR				
SD				
PD				

Table 11.3.4.2.5 Response rate estimates by IMWG (Independent Review assessment and “All Evaluable Patients” population)

	Arm A			Arm B		
	Proportion	Lower 95% limit	Upper 95% limit	Proportion	Lower 95% limit	Upper 95% limit
Response rate						

Binomial exact estimator and 95% confidence interval

Table 11.3.4.2.6 Response rate comparison by IMWG (Independent Review assessment and “All Evaluable Patients” population)

Response rate	Arm A		Arm B		Fisher exact test (p-value)
	N	%	N	%	
sCR+CR+VGPR+PR+MR					
SD+PD					

Table 11.3.4.2.7 Response rate by IMWG at early futility analysis (Independent Review assessment and “All Evaluable Patients” population)

Response	Arm A		Arm B	
	N	%	N	%
sCR				
CR				
VGPR				
PR				
MR				
SD				
PD				

Table 11.3.4.2.8 Response rate estimates without MR by IMWG (Independent Review assessment and “All Randomized Patients” population)

	Arm A			Arm B		
	Proportion	Lower 95% limit	Upper 95% limit	Proportion	Lower 95% limit	Upper 95% limit
Response rate						

Binomial estimates and 95% exact confidence interval

Table 11.3.4.2.9 Response rate comparison without MR by IMWG (Independent Review assessment and “All Randomized Patients” population)

Response rate	Arm A		Arm B		Fisher exact test (p-value)
	N	%	N	%	
sCR+CR+VGPR+PR					
MR+SD+PD+UK*					

(*) Including NE and insufficient data available.

Table 11.3.4.2.10 Response rate estimates without MR by IMWG (Independent Review assessment and “All Evaluable Patients” population)

	Arm A			Arm B		
	Proportion	Lower 95% limit	Upper 95% limit	Proportion	Lower 95% limit	Upper 95% limit
Response rate						

Binomial estimates and 95% exact confidence interval

Table 11.3.4.2.11 Response rate comparison without MR by IMWG (Independent Review assessment and “All Evaluable Patients” population)

Response rate	Arm A		Arm B		Fisher exact test (p-value)
	N	%	N	%	
sCR+CR+VGPR+PR					
MR+SD+PD					

Table 11.3.4.2.12 Median Time to Response (Independent Review assessment)

	Arm A		Arm B	
	Median	95% CI	Median	95% CI
Time to response*				

(*)sCR, CR, VGPR, PR or MR

Table 11.3.4.2.13 Median Time to Response without MR (Independent Review assessment)

	Arm A		Arm B	
	Median	95% CI	Median	95% CI
Time to response*				

(*)sCR, CR, VGPR or PR

11.3.4.3 Response rate by investigator assessment

Table 11.3.4.3.1 Response rate by IMWG (Investigator assessment and “All Randomized Patients” population)

Response	Arm A		Arm B	
	N	%	N	%
sCR				
CR				
VGPR				
PR				
MR				
SD				
PD				
Unknown*				

(*) Including NE and insufficient data available.

Table 11.3.4.3.2 Response rate estimates by IMWG (Investigator assessment and “All Randomized Patients” population)

	Arm A			Arm B		
	Proportion	Lower 95% limit	Upper 95% limit	Proportion	Lower 95% limit	Upper 95% limit
Response rate						

Binomial estimates and 95% exact confidence interval

Table 11.3.4.3.3 Response rate comparison by IMWG (Investigator assessment and “All Randomized Patients” population)

Response rate	Arm A		Arm B		Fisher exact test (p-value)
	N	%	N	%	
sCR+CR+VGPR+PR+MR					
SD+PD+UK*					

(*) Including NE and insufficient data available.

Table 11.3.4.3.4 Response rate by IMWG (Investigator assessment and “All Evaluable Patients” population)

Response	Arm A		Arm B	
	N	%	N	%
sCR				
CR				
VGPR				
PR				
MR				
SD				
PD				

Table 11.3.4.3.5 Response rate estimates by IMWG (Investigator assessment and “All Evaluable Patients” population)

	Arm A			Arm B		
	Proportion	Lower 95% limit	Upper 95% limit	Proportion	Lower 95% limit	Upper 95% limit
Response rate						

Binomial estimates and 95% exact confidence interval

Table 11.3.4.3.6 Response rate comparison by IMWG (Investigator assessment and “All Evaluable Patients” population)

Response rate	Arm A		Arm B		Fisher exact test (p-value)
	N	%	N	%	
sCR+CR+VGPR+PR+MR					
SD+PD					

Table 11.3.4.3.7 Response rate estimates without MR by IMWG (Investigator assessment and “All Randomized Patients” population)

	Arm A			Arm B		
	Proportion	Lower 95% limit	Upper 95% limit	Proportion	Lower 95% limit	Upper 95% limit
Response rate						

Binomial estimates and 95% exact confidence interval

Table 11.3.4.3.8 Response rate comparison without MR by IMWG (Investigator assessment and “All Randomized Patients” population)

Response rate	Arm A		Arm B		Fisher exact test (p-value)
	N	%	N	%	
sCR+CR+VGPR+PR					
MR+SD+PD+UK*					

(*) Including NE and insufficient data available.

Table 11.3.4.3.9 Response rate estimates without MR by IMWG (Investigator assessment and “All Evaluable Patients” population)

	Arm A			Arm B		
	Proportion	Lower 95% limit	Upper 95% limit	Proportion	Lower 95% limit	Upper 95% limit
Response rate						

Binomial estimates and 95% exact confidence interval

Table 11.3.4.3.10 Response rate comparison without MR by IMWG (Investigator assessment and “All Evaluable Patients” population)

Response rate	Arm A		Arm B		Fisher exact test (p-value)
	N	%	N	%	
sCR+CR+VGPR+PR					
MR+SD+PD					

Table 11.3.4.3.11 Median Time to Response (Investigator assessment)

	Arm A		Arm B	
	Median	95% CI	Median	95% CI
Time to response*				

(*)sCR, CR, VGPR, PR or MR

Table 11.3.4.3.12 Median Time to Response without MR (Investigator assessment)

	Arm A		Arm B	
	Median	95% CI	Median	95% CI
Time to response*				

(*)sCR, CR, VGPR or PR

11.3.4.4 Duration of response

Table 11.3.4.4.1 DR (Independent Review assessment and “All Responder Patients” population)

	Arm A	Arm B	Parameter	p-value
N				
Events				
Censored				
Median DR			Log-Rank: HR (95% CI) :	LR: HR:
DR at 6 months			Diff:	

Kaplan-Meier plot will be also shown (Figure 11.3.4.4.1)

Table 11.3.4.4.2 DR (Investigator assessment and “All Responder Patients” population)

	Arm A	Arm B	Parameter	p-value
N				
Events				
Censored				
Median DR			Log-Rank: HR (95% CI) :	LR: HR:
DR at 6 months			Diff:	

Kaplan-Meier plot will be also shown (Figure 11.3.4.4.2)

Table 11.3.4.4.3 DR without MR (Independent Review assessment and “All Responder Patients” population)

	Arm A	Arm B	Parameter	p-value
N				
Events				
Censored				
Median DR			Log-Rank: HR (95% CI) :	LR: HR:
DR at 6 months			Diff:	

Kaplan-Meier plot will be also shown (Figure 11.3.4.4.3)

Table 11.3.4.4.4 DR without MR (Investigator assessment and “All Responder Patients” population)

	Arm A	Arm B	Parameter	p-value
N				
Events				
Censored				
Median DR			Log-Rank: HR (95% CI) :	LR: HR:
DR at 6 months			Diff:	

Kaplan-Meier plot will be also shown (Figure 11.3.4.4.4)

Table 11.3.4.4.5 DR with PD confirmation (Independent Review assessment and “All Responder Patients” population)

	Arm A	Arm B	Parameter	p-value
N				
Events				
Censored				
Median DR			Log-Rank: HR (95% CI) :	LR: HR:
DR at 6 months			Diff:	

Kaplan-Meier plot will be also shown (Figure 11.3.4.4.5)

Table 11.3.4.4.6 DR with PD confirmation (Investigator assessment and “All Responder Patients” population)

	Arm A	Arm B	Parameter	p-value
N				
Events				
Censored				
Median DR			Log-Rank: HR (95% CI) :	LR: HR:
DR at 6 months			Diff:	

Kaplan-Meier plot will be also shown (Figure 11.3.4.4.6)

11.3.4.5 Analysis of crossover

Table 11.3.4.5.1 RR to combination treatment in patients who crossed over from Arm B to Arm A (“All Crossover Patients” population)

		After crossover (N,%)							
		sCR	CR	VGPR	PR	MR	SD	PD	NE
Before crossover	sCR								
	CR								
	VGPR								
	PR								
	MR								
	SD								
	PD								
	NE								

Table 11.3.4.5.2 Inpatient PFS comparison of patients who crossed over from Arm B to Arm A (“All Crossover Patients” population)

PFS	Before crossover	After crossover
Median		
PFS at 6 months		

Table 11.3.4.5.3 PFS comparison of patients (“All Randomized Patients” population)

PFS	Arm A	Arm B	
		Before crossover	After crossover
Median			
PFS at 6 months			

Listing 11.3.4.5.4 Best response and PFS before and after crossover.

Patient id.	Cycle of crossover	Best response		PFS	
		Before crossover	After crossover	Before crossover	After crossover
...					

Listing 11.3.4.5.5 Best response and PFS before in crossover patients.

Patient id.	Independent review assessment				Investigator assessment			
	Best response	PFS	PFS event	PD confirmation	Best response	PFS	PFS event	PD confirmation
...								

Table 11.3.4.5.6 Time to crossover

	N	Median	Min	Max
Time to crossover (months)				

Table 11.3.4.5.7 Baseline characteristics comparison patients without crossover vs crossover

Variable**	Value	N	Without Crossover	Crossover	p-value*
Sex	F	XXX	XX (XX.X%)	XX (XX.X%)	X.XXXX
	M	XXX	XX (XX.X%)	XX (XX.X%)	
Age	Median(range)	XXX	XX.X (XX-XX)	XX.X (XX-XX)	X.XXXX
...					

(*)Fisher's exact test (categorical variables); Mann-Whitney-Wilcoxon (continuous variables)

(**)Sex, age, PS (ECOG), BSA, Durie Salmon stage, International Staging System, Secretary/Non-secretory, MM type, time from diagnosis, time from last PD, number of prior lines, status to prior therapy, status to prior bortezomib therapy, status to prior thalidomide/lenalidomide therapy, status to prior IMiD therapy, status to prior PIs therapy, stem cell transplantation, plasma cells, hemoglobin, creatinine, calcium, genetic risk, lytic lesions and plasmacytomas.

11.3.4.6 Follow-up

Table 11.3.4.6.1 Median FU for PFS

	Arm A		Arm B	
	Median	95% CI	Median	95% CI
Follow-up				

Table 11.3.4.6.2 Median FU for OS

	Arm A		Arm B	
	Median	95% CI	Median	95% CI
Follow-up				

11.3.4.7 Symmetry of evaluations

Table 11.3.4.7.1 Time to MM assessments

MM assessment	Treatment group	n	Median (days)	Wilcoxon p-value
1	Arm A			
	Arm B			
2	Arm A			
	Arm B			
...	Arm A			
	Arm B			

This table will be complemented with a boxplot showing the time to first, second, third and further MM assessments by treatment arm (Figure 11.3.4.7.1).

Table 11.3.4.7.2 Time to first assessment

	Arm A	Arm B	Parameter	p-value
N				
Events				
Censored				
Median to first assessment			Log-Rank: HR (95% CI) :	LR: HR:

Kaplan-Meier plot will be also shown (Figure 11.3.4.7.2)

Table 11.3.4.7.3 Time to second assessment

	Arm A	Arm B	Parameter	p-value
N				
Events				
Censored				
Median second assessment			Log-Rank: HR (95% CI) :	LR: HR:

Kaplan-Meier plot will be also shown (Figure 11.3.4.7.3)

11.3.4.8 Univariate analyses

Table 11.3.4.8.1 Univariate analysis of PFS (Independent Review assessment and “All Randomized Patients” population)

	Arm A			Arm B			p-value*
	Median (months)	Lower 95% Confidence Limit	Upper 95% Confidence Limit	Median (months)	Lower 95% Confidence Limit	Upper 95% Confidence Limit	
Prognostic factors**							
Gender							
Age							
...							

(*) Cox regression. (**) See covariate listing in section 6.2.3. A forest plot with the summary of HR will be also shown (Figure 11.3.4.8.1)

Table 11.3.4.8.2 Univariate analysis of PFS (Investigator Assessment and “All Randomized Patients” population)

	Arm A			Arm B			p-value*
	Median (months)	Lower 95% Confidence Limit	Upper 95% Confidence Limit	Median (months)	Lower 95% Confidence Limit	Upper 95% Confidence Limit	
Prognostic factors**							
Gender							
Age							
...							

(*) Cox regression. (**) See covariate listing in section 6.2.3. A forest plot with the summary of HR will be also shown (Figure 11.3.4.8.2)

Table 11.3.4.8.3 Univariate analysis of OS (Independent Review assessment and “All Randomized Patients” population)

Prognostic factors**	Arm A			Arm B			p-value*
	Median (months)	Lower 95% Confidence Limit	Upper 95% Confidence Limit	Median (months)	Lower 95% Confidence Limit	Upper 95% Confidence Limit	
Gender							
Age							
...							

(*) Cox regression. (**) See covariate listing in section 6.2.3. A forest plot with the summary of HR will be also shown (Figure 11.3.4.8.3)

Table 11.3.4.8.4 Univariate analysis of OS (Investigator Assessment and “All Randomized Patients” population)

Prognostic factors**	Arm A			Arm B			p-value*
	Median (months)	Lower 95% Confidence Limit	Upper 95% Confidence Limit	Median (months)	Lower 95% Confidence Limit	Upper 95% Confidence Limit	
Gender							
Age							
...							

(*) Cox regression. (**) See covariate listing in section 6.2.3. A forest plot with the summary of HR will be also shown (Figure 11.3.4.8.4)

Table 11.3.4.8.5 Univariate analysis of RR (Independent Review assessment and “All Randomized Patients” population)

Prognostic factors**	Arm A				Arm B				p-value*
	N	RR	Proportion (%)	95% CI	N	RR	Proportion (%)	95% CI	
Gender									
Age									
...									

(*) Logistic regression. (**) See covariate listing in section 6.2.3. A forest plot with the summary of ORR confidence intervals will be also shown (Figure 11.3.4.8.5)

Table 11.3.4.8.6 Univariate analysis of RR (Investigator Assessment and “All Randomized Patients” population)

Prognostic factors**	Arm A				Arm B				p-value*
	N	RR	Proportion (%)	95% CI	N	RR	Proportion (%)	95% CI	
Gender									
Age									
...									

(*) Logistic regression. (**) See covariate listing in section 6.2.3. A forest plot with the summary of ORR confidence intervals will be also shown (Figure 11.3.4.8.6)

Table 11.3.4.8.7 Univariate analysis of PFS with PD confirmation (Independent Review assessment and “All Randomized Patients” population)

Prognostic factors**	Arm A			Arm B			p-value*
	Median (months)	Lower 95% Confidence Limit	Upper 95% Confidence Limit	Median (months)	Lower 95% Confidence Limit	Upper 95% Confidence Limit	
Gender							
Age							
...							

(*) Cox regression. (**) See covariate listing in section 6.2.3. A forest plot with the summary of HR will be also shown (Figure 11.3.4.8.7)

11.3.4.9 Multivariate analyses

Table 11.3.4.9.1 Multivariate analysis of PFS (Independent Review assessment and “All Randomized Patients” population)

Analysis of Maximum Likelihood Estimates*								
Variable Label	Variable values	DF	Parameter Estimate	Standard Error	Chi-Square	Pr > ChiSq	Hazard Ratio	95% Hazard Ratio Confidence Limits

* Cox regression
See list of covariates in section 6.2.3

Table 11.3.4.9.2 Multivariate analysis of PFS (Investigator assessment and “All Randomized Patients” population)

Analysis of Maximum Likelihood Estimates*								
Variable Label	Variable values	DF	Parameter Estimate	Standard Error	Chi-Square	Pr > ChiSq	Hazard Ratio	95% Hazard Ratio Confidence Limits

* Cox regression
See list of covariates in section 6.2.3

Table 11.3.4.9.3 Multivariate analysis of RR (Independent Review assessment and “All Evaluable Patients” population)

Analysis of Maximum Likelihood Estimates*								
Variable Label	Variable values	DF	Parameter Estimate	Standard Error	Chi-Square	Pr > ChiSq	Odds Ratio	95% Odds Ratio Confidence Limits

* Logistic regression
See list of covariates in section 6.2.3

Table 11.3.4.9.4 Multivariate analysis of RR (Investigator assessment and “All Evaluable Patients” population)

Analysis of Maximum Likelihood Estimates*								
Variable Label	Variable values	DF	Parameter Estimate	Standard Error	Chi-Square	Pr > ChiSq	Odds Ratio	95% Odds Ratio Confidence Limits

* Logistic regression

See list of covariates in section 6.2.3

Table 11.3.4.9.5 Multivariate analysis of OS (“All Randomized Patients” population)

Analysis of Maximum Likelihood Estimates*								
Variable Label	Variable values	DF	Parameter Estimate	Standard Error	Chi-Square	Pr > ChiSq	Hazard Ratio	95% Hazard Ratio Confidence Limits

* Cox regression

See list of covariates in section 6.2.3

Table 11.3.4.9.6 Multivariate analysis of PFS by region (Independent Review assessment and “All Randomized Patients” population)

Analysis of Maximum Likelihood Estimates*								
Variable Label	Variable values	DF	Parameter Estimate	Standard Error	Chi-Square	Pr > ChiSq	Hazard Ratio	95% Hazard Ratio Confidence Limits

* Cox regression

See list of covariates in section 6.2.3

Table 11.3.4.9.7 Multivariate analysis of PFS with PD confirmation (Independent Review assessment and “All Randomized Patients” population)

Analysis of Maximum Likelihood Estimates*								
Variable Label	Variable values	DF	Parameter Estimate	Standard Error	Chi-Square	Pr > ChiSq	Hazard Ratio	95% Hazard Ratio Confidence Limits

* Cox regression

See list of covariates in section 6.2.3

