10.2.3.2 Patients' Evaluability for Response

All patients who have completed at least one evaluable cycle or who have received two uncompleted cycles followed by at least one response assessment not less than eight weeks (\pm one week) after treatment onset, will be considered evaluable for response. In addition, any eligible patients who receive at least one treatment cycle or have received two uncompleted cycles and experience disease progression or die due to progressive disease prior to response evaluation will be considered evaluable for response and will be categorized as an "early progression".

Patients withdrawn due to drug-related toxicity without any tumor assessments after the start of study treatment will be considered as "treatment failures".

Patients withdrawn due to significant clinical deterioration of unknown reason, hypersensitivity reactions, or refusal to continue on study for any reason or unrelated AEs without any disease assessments after the start of study treatment will be considered not evaluable for efficacy and their response will be categorized as "non evaluable".

Binomial estimates with exact 95% CIs will be calculated for the analysis of response rate. Randomized patients not evaluable for response will be excluded from the denominator exclusively for the futility analysis but will be included in all final efficacy analyses.

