The following time-dependent covariates will be included in the IPCW analysis: ECOG, Body Surface Area (BSA), m-protein value (serum/urine), number of adverse events grade \geq 3, bone marrow plasma cells, creatinine, LDH, hemoglobin and corrected serum calcium. Also, baseline covariates such as gender, age, MM type (i.e.: IgG, IgA, light chain myeloma, non-secretory), number of prior lines of anticancer treatment, status (relapsed vs. relapsed/refractory), refractory status to bortezomib, lenalidomide/thalidomide prior therapy, refractory status to last prior therapy, refractory status to IMiD therapy, refractory status to PIs therapy, genetic risk, previous SCT, time from diagnosis to randomization, time from last progression before randomization, International Staging System, Durie-Salmon stage, presence of plasmacytomas, presence of lytic lesions, number of plasmacytomas, sum of the dimensions of plasmacytomas, will be included.

The reasons for censoring of OS will be shown using counts and percentages.

An analysis will be carried out in the subpopulation of patients without crossover or subsequent therapy in order to investigate the isolated effect of study treatments in survival in this subpopulation. It will be also carried out in the subpopulation of patients without crossover or subsequent therapy and with event in the primary analysis of PFS by IRC.

Response rate:

Binomial estimates with exact 95% CIs will be calculated for the analysis of response rate. Randomized patients not evaluable for response will be excluded from the denominator exclusively for the futility analysis, but will be included in all the final efficacy analyses. A supportive analysis will be also done in the “All Evaluable Patients” population.

The magnitude of response, in patients with secretory MM, will be described by waterfall plots showing the best M-spike reduction from baseline.

A supportive analysis of response rate will be performed taking into account PR or better as best overall response based on the IMWG criteria.

Duration of response:

Duration of objective response will be analyzed according to the Kaplan-Meier method and compared between treatment groups using the log-rank test.

DR requiring confirmation of PD for determination of PFS will be analyzed according to the Kaplan-Meier method and compared between treatment groups using the log-rank test.

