Univariate evaluation of the influence of different prognostic factors on the main efficacy endpoints will be performed by using the following covariates: Gender, age, baseline ECOG, Body Surface Area (BSA), MM type (i.e.: IgG, IgA, light chain myeloma, non-secretory), number of prior lines of anticancer treatment, status (relapsed *vs.* relapsed/refractory) refractory status to bortezomib, lenalidomide/thalidomide prior therapy, refractory status to last prior therapy, refractory status to IMiD therapy, refractory status to PIs therapy, genetic risk, previous SCT, time from diagnosis to randomization, time from last progression before randomization, International Staging System, Durie-Salmon stage, bone marrow plasma cells, bone lytic lesions (Y/N), plasmacytomas at baseline (Y/N), number of lesions at baseline, sum of the dimensions of plasmacytomas, creatinine (≥ 2 mg/dl *vs.* < 2 mg/dl), LDH, hemoglobin and corrected serum calcium (>11.5 mg/100ml *vs.* ≤ 11.5 mg/100ml).

Exploratory subgroup analyses will be performed by means of logistic regression, Kaplan-Meier analysis and Cox regression. The different subgroup analyses will be summarized by means of Forest plots.

Cox proportional hazard models for PFS and OS and logistic regression models for RR will include the prognostic factors specified for the univariate analysis. More relevant and explanatory covariates from the univariate analysis will be included in the multivariate analyses (p-value < 0.10). Prognostic factors with more than 10% missing values will be excluded in the multivariate analyses.

The analyses above mentioned will be also performed for the sensitivity analysis of PFS with confirmation of PD by IRC.

In addition, and in order to check if there are differences in the main efficacy endpoint between different continents/geographical areas, multivariate analyses of PFS by IRC, adding region as a covariate, will be performed. The variable “region” will be created with four categories (Europe, Asia, Oceania, and USA) and then three Cox regressions will be performed.

- 1) PFS by IRC with arm, region and interaction term.
- 2) PFS by IRC with arm and region as main effects.
- 3) Full model selected in the multivariate analysis of PFS by IRC, including region as variable.

Symmetry of evaluations.

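### The multivariate response-rate models are set only on All Evaluable Patients, against the plan's own rule for final efficacy analyses

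*SAP*

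**What the plan says.** SAP 11.3.4.9 has two multivariate models of response rate. The first is titled "Table 11.3.4.9.3 Multivariate analysis of RR (Independent Review assessment and “All Evaluable Patients” population"; the second, Table 11.3.4.9.4, is the investigator-assessed counterpart on the same population. Neither has an All Randomized version.

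The text of both documents sets a different rule. Under SAP 6.2.3 (Response rate), randomized patients who are not evaluable are "excluded from the denominator exclusively for the futility analysis, but will be included in all the final efficacy analyses", and the evaluable-set analysis is described there as supportive. Protocol 10.2.3.2 gives the same rule: such patients leave the denominator at futility alone, "but will be included in all final efficacy analyses".

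The covariates for these models are screened in the univariate tables at p < 0.10 (SAP 6.2.3). Those tables use the randomized set: "Table 11.3.4.8.5 Univariate analysis of RR (Independent Review assessment and “All Randomized Patients” population", with Table 11.3.4.8.6 doing the same for the investigator assessment.

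**The concern.** All Evaluable Patients is defined in SAP 4.1 by what happens after randomization: cycles completed, response assessments made, and the reason for withdrawal. A model restricted to that set no longer compares groups formed by randomization. Any factor linked to becoming non-evaluable, treatment arm included, can have its odds ratio changed by the restriction alone.

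There is a plausible route to imbalance between arms. SAP 4.1 and Protocol 10.2.3.2 class patients withdrawn for hypersensitivity reactions without a later disease assessment as non-evaluable. Protocol 1.3.3.2 describes such reactions with plitidepsin and thinks them probably related to its formulation, and only Arm A receives plitidepsin before crossover. That route would remove Arm A non-responders. Other listed routes, such as refusal or unexplained deterioration, could work the other way.

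There is also a mismatch within the modelling: covariates are chosen in one population and fitted in another.

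**Working it through.** **1. Populations side by side.** The plan states no N and no evaluability rate for these models, so there is no figure of its own to reproduce. The check is first one of text.

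| Analysis | SAP tables | Population |
|---|---|---|
| Main response comparison | 11.3.4.2.3, 11.3.4.3.3 | All Randomized; unknown grouped with SD and PD |
| Supportive response comparison | 11.3.4.2.6, 11.3.4.3.6 | All Evaluable |
| Univariate response | 11.3.4.8.5, 11.3.4.8.6 | All Randomized |
| Multivariate response | 11.3.4.9.3, 11.3.4.9.4 | All Evaluable only |
| Multivariate PFS and OS | 11.3.4.9.1, 11.3.4.9.2, 11.3.4.9.5, 11.3.4.9.6, 11.3.4.9.7 | All Randomized |

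The two multivariate response tables are the only row in which the evaluable set appears without a randomized counterpart.

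**2. What the restriction can do to an odds ratio.** Let r be the share of randomized patients in an arm who respond and e the share who are non-evaluable. Non-evaluable patients have no response by definition. Then:

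- odds of response, all randomized = r / (1 − r)
- odds of response, evaluable only = r / (1 − e − r)

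Assume r = 30% in Arm A and 10% in Arm B. These are illustrative values, not document figures. In all randomized patients, OR = (0.30/0.70) / (0.10/0.90) = 3.86.

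| Non-evaluable, Arm A / Arm B (assumed) | Evaluable-set OR | Change from 3.86 |
|---|---|---|
| 10% / 10% | (0.30/0.60) / (0.10/0.80) = 4.00 | +4% |
| 15% / 5% | (0.30/0.55) / (0.10/0.85) = 4.64 | +20% |
| 5% / 15% | (0.30/0.65) / (0.10/0.75) = 3.46 | −10% |

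The shift depends mainly on which arm loses more patients. These odds ratios are unadjusted and are for arm. The same algebra applies to a prognostic factor, with its levels in place of the arms.

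**3. Patients lost.** On the planned 250, assumed non-evaluable shares of 5%, 10% and 20% would leave 238, 225 and 200 in the model.

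**The case against.** The best defence is that All Evaluable Patients is a prespecified set for final response rate: SAP 4.2 and the definition of objective response rate in SAP 6.1.2 name both sets. That is true, but naming both does not justify giving only the one that SAP 6.2.3 calls supportive.

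Second, the evaluable set is less selective than its name suggests. Under SAP 4.1, patients withdrawn for early progression or treatment-related toxicity have their own categories, even without a full cycle. This stands and limits how many patients leave. It does not cover hypersensitivity, refusal, unexplained deterioration, unrelated adverse events without assessment, or disqualifying protocol deviations.

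Third, little depends on these models. The response comparison between arms already exists in all randomized patients. SAP 8.7 gives the purpose of the multivariate analysis as the influence of strata and prognostic factors, and outside the region models of PFS the SAP does not explicitly name arm as a term. This also stands: it limits the consequence but does not remove the contradiction.

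A reader might infer more, namely that the multivariate models in general abandon the randomized population and that every one of them drops patients with a missing covariate. The documents do not support either. Five of the seven multivariate tables are on the randomized set, for example "Table 11.3.4.9.1 Multivariate analysis of PFS (Independent Review assessment and “All Randomized Patients” population" and "Table 11.3.4.9.5 Multivariate analysis of OS (“All Randomized Patients” population". On missing covariates the SAP says "Prognostic factors with more than 10% missing values will be excluded in the multivariate analyses", and SAP 8.8 only governs tabulation. Nothing is stated about a patient who lacks a value in a retained factor. Deletion of such patients would be an inference from software defaults. Its size is also open: with k retained factors each missing in a share m of patients, independent missingness keeps (1 − m)^k. That is 95% (238 of 250) at m = 1%, k = 5, and 43% (108 of 250) at m = 10%, k = 8. If the same 10% of patients miss every factor, 90% (225) remain; if the factors are complete, nobody is lost. The first two region models contain only arm, region and, in one of them, their interaction, so they have little to lose.

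**Conclusion.** Tables 11.3.4.9.3 and 11.3.4.9.4 are wrong as written. They contradict Protocol 10.2.3.2 and SAP 6.2.3, and they use a different population from the tables that select their covariates.

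The contradiction is a matter of text and rests on no assumption. The size of any effect cannot be derived, because the documents report neither evaluability nor response by arm. The range of 3.46 to 4.64 around 3.86 rests entirely on the assumed rates and shows only that the shift can go either way.

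The primary log-rank test of PFS, the OS test and the main response comparison do not change. Handling of missing values in retained covariates is unstated detail, not a demonstrated error.

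**What to change.** Set Tables 11.3.4.9.3 and 11.3.4.9.4 on All Randomized Patients, counting unknown or non-evaluable patients as non-responders, as Tables 11.3.4.2.3 and 11.3.4.3.3 already do. Keep the All Evaluable versions as added supportive tables.

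The cost is two retitled tables, two supportive ones and a rerun of two logistic models; no new data are needed. The protocol's notes record the PFS endpoint as fulfilled and an OS analysis done on 19 May 2017. If the response models have already been run, the randomized-set versions should be added and documented as a correction, with both sets reported.

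Optional clarification: print the N and the number of events or responders used in each multivariate model, state how missing values in retained covariates are handled, and say whether arm is forced into each model. Multiple imputation is not needed for this correction; combined with selection at p < 0.10 it would need its own rules for selection and pooling.
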